In the same way that social-work interventions have proven beneficial for patients with cancer, such interventions can enhance outcomes in those affected by glaucoma and other eye diseases. Medical social workers understand and value a patient's right to self-determination. They can work with patients directly to empower them to seek appropriate methods of treatment and follow-up vision care. Therefore, we have budgeted for one part-time, medical social worker who will assist the research team with identifying cultural, racial/ethnic, costs, trust, and language barriers as described by Bentacourt. She will work interact with any social workers employed at the FQHCs; supervise, train, and mentor the patient navigators; and contact patients enrolled in the enhanced intervention group. By testing and refining our approaches to removing these barriers, we hypothesize that patient navigators and a social worker will significantly improve patients' follow-up vision care, patient satisfaction, and quality-of-life.

C.9. Management and Follow-up Visits 3-8: To ensure that all patients receive appropriate treatment and that outcomes are tracked yearly, adherence to follow-up eye care access and utilization will be our primary outcome measure. All patients who fulfill the inclusion criteria, have consented, and completed Visit 2 will be randomized and either referred or scheduled (depending on assigned randomization) for Visit 3 within 4 weeks with a local, general eye care provider or earlier at the glaucoma specialist’s discretion. All medical records from our confirming diagnostic exam will be faxed to the local eye care provider who will examine the patient. A form acknowledging receipt of records by the local eye care provider will be requested (requiring signature). Participating eye care providers will be informed about the study during Phase 1 and blinded to the patient’s intervention group. We will refer patients diagnosed with glaucoma or glaucoma suspect to an office that is able to conduct visual field testing.

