## **E.2. Data Analysis for Aims 1 and 2**

**E.2.a. Primary Analysis for Aim 1:** The primary analysis for Aim 1 will be to estimate the positive predictive value (PPV) of the teleophthalmology intervention for diagnosing of glaucoma. We hypothesize that the diagnosis of glaucoma and glaucoma suspect using undilated optic disc images, tonometry pressure results, and medical history will predict the comprehensive eye exam diagnosis. That is, we will calculate the proportion of patients diagnosed with glaucoma or glaucoma suspect whose diagnosis was confirmed at Visit 2 with an exact two-sided binomial confidence interval. We will conclude that the telemedicine intervention has good performance if the lower bound of the confidence interval is above 80%.

The expected sample size for this aim is 250 patients as we anticipate approximately 50% of those diagnosed with eye pathology and who return for the confirmation Visit 2 will have been diagnosed with glaucoma or glaucoma suspect at Visit 1. Data from Maa (2014) can be used to estimate the PPV for glaucoma at 85%. With 250 patients, we have 50% power to conclude the PPV is greater than 80% if the true PPV is 85% and over 99% power to conclude the PPV is greater than 80% if the true PPV is 90% using a 2-sided test with alpha=0.05. We will repeat this analysis looking at the proportion of patients diagnosed with eye pathology who in fact have an ocular diagnosis (whether or not the exact abnormality was correct).

**E.2.b. Primary Outcome Measure for Aim 2:** Patient baseline demographic and clinical characteristics will be summarized overall and by randomization assignment (in Aim 2) using means, medians, standard deviations, and ranges or frequencies and percentages, as appropriate. Our general approach from the randomized trial is to analyze patients as randomized regardless of the amount of intervention received. The primary outcome measure for Aim 2 is attendance at recommended follow-up visits (Visit 4 and later). Since the expected

number of appointments will differ based on diagnosis and disease severity, which may change over time, attendance will be summarized annually.

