For each year under observation, an expected number of visits will be determined based on the recommended follow-up at the first visit for that year (Table 9). For purposes of this calculation, attendance at appointments within 13 months of the first visit will be assessed. We recognized that follow-up recommendations will vary for each patient depending on eye pressure control, medication adherence, disease severity, and surgery/laser appointments. Therefore, the research team, in conjunction with [name] and the CDC, will plan and develop definitions of adherence for patients during Visits 3-8.

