**Table 9: Assessment of Adherence to Follow-Up Recommendations**

Recommended Follow-up	Number of visits per year considered adherent to recommendations
1-2 months	At least 6 visits per year with an eye care provider
3-6 months	At least 3 visits per year with an eye care provider
6 months	At least 2 visits per year with an eye care provider
12 months	At least 1 visit per year with an eye care provider

E.2.c. Primary Analysis for Aim 2: The primary outcome of the study is adherence to recommended follow-up in each year as described in section E.1.c. For each of the 3 years of follow-up, we have a dichotomous measure of adherence. We will model this longitudinal dichotomous outcome using Poisson regression within a generalized estimating equation (GEE) framework. Our model will include time (Year 1, 2, and 3), randomization assignment, randomization by treatment interaction, and baseline individual characteristics believed to be associated with adherence to follow-up, including age, diagnosis, vision impairment, and overall vision-related quality-of-life. Within this model, we will test 2 hypotheses.

First, we will compare randomization groups at Year 1 to test whether there are differences in early adherence. Second, we will calculate the average effect of randomization across Years 2 and 3 and test the long-term efficacy of the intervention. In both cases, we will estimate the overall relative risk of adherence along with its associated confidence interval. Each test will be performed with alpha=0.025. The primary analysis will include all patients who were randomized and have some adherence data (see section on missing data below).

E.2.d. Power for the Primary Analysis for Aim 2: Our estimated available sample size is given in Figure 2. We will randomize 300 patients (150 per group). Assuming up to 10% dropout where adherence cannot be calculated due to death or study withdrawal (i.e., final analysis dataset of n=135 per group), we calculate power to detect a 20% improvement in adherence under various assumptions of adherence under Usual Care. We have greater than 80% power to detect these differences using a two-sided chi-square test with alpha=0.025 (Table 10).

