**Table 10: Determination of Power Calculation**

Percent Adherence Under Usual Care	Percent Adherent Under Enhanced Intervention	Relative Risk	Power
35%	55%	1.57	86%
40%	60%	1.5	86%
45%	65%	1.44	86%
50%	70%	1.4	87%
55%	75%	1.36	89%
60%	80%	1.33	92%

E.2.e. Secondary Analyses for Aim 2: We will perform a secondary analysis to test for differences in the average number of appointments kept per person-year of follow-up. We will use Poisson regression to model

the total number of appointments after Visit 3 by randomization assignment. The offset term will be time under observation measured from Visit 3 to end of follow-up. We will adjust baseline for age, diagnosis, vision impairment, and vision-related quality-of-life. Change in continuous clinical and quality-of-life measures (IOP, visual acuity, NEI-VFQ, etc) will be modeled using mixed effects linear regression. Fixed effects will be time (treated continuously), randomization assignment, treatment by time interaction, age, and diagnosis. A first-order autoregressive correlation structure will be assumed to model correlation among repeated measurements. When possible, random slope and intercept terms may also be included. Effects of intervention on these measures will be tested by the significance of the interaction term.

E.2.f. Exploratory Analyses for Aim 2: We will consider whether the effect of the intervention differs by baseline patient characteristics of glaucoma severity (using VF mean deviation), and vision-related quality-of-life (NEI VFQ score). The primary model will be extended to include the interaction between these variables and randomization assignment to allow for estimation of intervention effects by baseline categories.

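### The secondary visit-rate model starts its clock at Visit 3, a post-randomisation event, so it compares Visit 3 attenders rather than the randomised groups

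*Combined protocol and SAP*

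**What the plan says.** E.2.e (Secondary Analyses for Aim 2) compares the average number of appointments kept per person-year. The count is "the total number of appointments after Visit 3 by randomization assignment", and "The offset term will be time under observation measured from Visit 3 to end of follow-up". The model adjusts for baseline age, diagnosis, vision impairment and vision-related quality of life.

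Randomisation comes before Visit 3. Under C.9, patients who have consented and completed Visit 2 are randomised and "either referred or scheduled (depending on assigned randomization) for Visit 3 within 4 weeks". Under C.5.c, patients with high eye pressure at Visit 1 are randomised then and skip Visit 2. C.8 lists phoning patients to schedule appointments and arranging transport among the navigators' tasks.

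The stated principle in E.2.b is: "Our general approach from the randomized trial is to analyze patients as randomized regardless of the amount of intervention received".

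For the primary outcome, E.2.b says that "an expected number of visits will be determined based on the recommended follow-up at the first visit for that year" and that "attendance at appointments within 13 months of the first visit will be assessed". The lowest threshold in Table 9 is "At least 1 visit per year with an eye care provider". E.2.g scores loss of contact as non-adherent and expects missing outcomes only from death or formal withdrawal.

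**The concern.** Attendance at Visit 3 is something the intervention is designed to change. A model whose clock starts there has no start date, and so no person-time, for a randomised patient who never arrives. E.2.e offers no substitute start and no rule for entering such a patient with a count of zero. The fitted comparison is then between two groups selected after randomisation, by routes that differ by arm.

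Two things are at stake. Any gain from bringing more patients to their first appointment is removed from the rate ratio. Also, the patients whom navigation brings in enter the enhanced arm's denominator with no counterpart in usual care. If they attend less often afterwards, they lower that arm's average rate.

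**Working it through.** **Plan's own figure.** The plan states no power or expected ratio for this secondary model. Table 10 concerns the primary comparison. It reproduces at 135 per group, two-sided alpha 0.025: 86.1, 85.7, 86.1, 87.2, 89.1 and 91.6% against the stated 86, 86, 86, 87, 89 and 92%. No stated figure is questioned here.

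**Inputs.** From the documents: count and offset (E.2.e), timing of randomisation (C.9, C.5.c), 150 per group (E.2.d). Assumed: Visit 3 attendance by arm, later visit rates, equal follow-up time in the two arms, and that everyone who would attend under usual care would also attend under navigation. The illustration is unadjusted.

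**Relation between the two ratios.** Let S be visits after Visit 3 per randomised patient and p the proportion attending Visit 3, with 1 = enhanced and 2 = usual care.

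- As randomised: S1/S2.
- As written: (S1/p1)/(S2/p2) = (S1/S2) × (p2/p1).

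The factor p2/p1 does not depend on later visit rates:

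- 97% vs 95%: 0.95/0.97 = 0.979
- 90% vs 80%: 0.80/0.90 = 0.889
- 48% vs 30%: 0.30/0.48 = 0.625

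The last pair is appointment attendance in the earlier navigator trial in patients with diabetes (C.3.b). It is not Visit 3 attendance in this trial and serves only as an outer case.

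**Worked ratios.** Patients who attend either way make 2 visits a year in both arms (no gain among them). Patients brought in by navigation make r visits a year. At 90% vs 80% and r = 1:

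- S1 = 0.8×2 + 0.1×1 = 1.7 and S2 = 0.8×2 = 1.6
- As randomised: 1.7/1.6 = 1.0625
- As written: (1.7/0.9)/(1.6/0.8) = 1.889/2 = 0.944

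| Visit 3 attendance, enhanced vs usual | r | As written | As randomised |
|---|---|---|---|
| 97% vs 95% | 1 | 0.990 | 1.92/1.90 = 1.011 |
| 90% vs 80% | 1 | 0.944 | 1.0625 |
| 90% vs 80% | 2 | 1.000 | 1.125 |
| 90% vs 80% | 3 | 1.056 | 1.1875 |
| 48% vs 30% | 1 | 0.8125 | 0.78/0.60 = 1.30 |
| 48% vs 30% | 2 | 1.000 | 0.96/0.60 = 1.60 |

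Both columns count the same visits, those after Visit 3, so the difference is due to the clock and the analysis set alone.

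**Patients without an offset.** At 150 per group and 90% vs 80%: 300 − (135 + 120) = 45. At 48% vs 30%: 300 − (72 + 45) = 183.

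**The case against.** E.2.e states no exclusion. Visit 3 is due within four weeks (C.9) and missed visits are recorded (E.1.c), so an analyst could start the clock at a due date and keep everyone. That is fair: the loss of non-attenders is a consequence of the wording, not a stated rule. But the text names no due date as the start, and an appointment date that is booked in one arm and left to the patient in the other would not be a neutral one.

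The effect may also be small. At 97% vs 95% the factor is 0.98, and the analysis is secondary. Both points stand. Baseline adjustment does not answer the concern, since it cannot restore patients who have no person-time.

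A reader might go further in four ways that the documents do not support:

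- **That navigation will look harmful.** With no other gain, the ratio falls below 1 only if brought-in patients visit less often than the others. At equal rates it is exactly 1.00.
- **That the primary outcome leaves an in-contact patient with no first visit unscored.** The quota and window in E.2.b do hang on the first visit of the year, and E.2.g names only loss of contact. But E.2.d and E.2.g confine incalculable or missing adherence to death and withdrawal, and zero visits fails every row of Table 9. What is missing is an explicit sentence; the plan already implies a non-adherent score.
- **That this score would be settled after seeing results.** C.5.d commits to adherence definitions before the study begins. Their absence from these documents does not show otherwise.
- **That survey phone calls keep more non-attenders in contact in the enhanced arm.** C.6.b ties those surveys to a window around a follow-up visit, so they show no extra contact with patients who have no visit.

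**Conclusion.** The point holds for the secondary model. As written, E.2.e conditions on Visit 3 attendance, which follows randomisation and is a target of the intervention, and this departs from the as-randomised approach in E.2.b. Whenever attendance is higher under navigation, the ratio is pulled down by exactly the ratio of attendances, given equal follow-up: from about 2% at 97% vs 95% to 11% at 90% vs 80%. If Visit 3 attendance resembled the earlier navigator trial, the pull would be 37.5%. The true size cannot be known from the documents, which give no Visit 3 attendance for this trial.

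It should be fixed before analysis. It does not touch Table 10 or the primary test. On the primary outcome, only a clarifying sentence is needed.

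**What to change.** In E.2.e:

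- Start the offset at randomisation, or at a fixed Visit 3 due date applied identically in both arms. Randomisation is simpler.
- Include every randomised patient, keeping zero counts for those who never attend Visit 3.
- Keep counting visits after Visit 3, which stays in line with the primary outcome's restriction to Visit 4 onward.
- Use robust standard errors. Table 9 expects between 1 and 6 visits a year, so counts are likely to vary more than a Poisson model allows.
- Report the Visit 3 version as supplementary, labelled as a comparison among Visit 3 attenders.

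In E.2.g, as a minor clarification, add one sentence: a living, non-withdrawn randomised patient with no eye-care visit in a year is scored non-adherent for that year.

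The cost is SAP wording and slightly more analysis work. Visits kept and missed are already recorded per patient (E.1.c), so no new data are needed. The estimand changes to visits per randomised person-year, and the report should say so.

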**C.6.a. National Eye Institute-Visual Function Questionnaire (NEI-VFQ):** A member of the research team will consent all patients and administer the validated NEI-VFQ-25 questionnaire at Visit 2, Visit 5 and Visit 8 to assess barriers and the influence of their vision impairment on their health-related quality-of-life. The 12 subscales are calculated by adding the relevant items and transforming the scores into a scale from 0 to 100. Higher scores indicate better quality-of-life. The composite score will be calculated as the average of 12 subscale scores. Patient navigators will use these results to assess barriers and refer patients to appropriate professionals, such as a social worker, low vision specialist, psychiatrist, occupational therapist, Medicare/Medicaid insurance advisor, and/or cataract surgeon. All materials will be culturally and linguistically appropriate and translated into other languages as necessary using trained medical interpreters and we will track all process measures.

\*NEIVFQ surveys will be administered in person to all patients at Visit 2. For Visits 5 and 8 questionnaires will be administered over the phone by a patient navigator or social worker.

**C.6.b. Patient Satisfaction Survey:** With assistance from Westat, our partners, and Advisory Board members, we will create a new survey instrument and administer it at the end of each of the study visits. We will ask patients to rate their satisfaction with the exam, its duration, its convenience, the staff, and the likelihood of attending a follow-up eye exam. These surveys will optimize patient engagement and report outcomes that are important to patients and stakeholders.

\*Satisfaction surveys will be administered in person to all patients for Visits 1 and 2. For Visit 5 surveys will be administered over the phone by a patient navigator or social worker for all enrolled patients. For Visits 3, 4, 6, and 7 satisfaction surveys will be administered according to randomization. For Visit 8 (or final visit), a Study Closeout Satisfaction Survey will be administered at the primary care office by a member of the study team.

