**D.1.b. Effectiveness/Efficacy:** We will evaluate the impact of our enhanced intervention on our proposed outcomes, including quality-of-life, and economic efficiency. Determining the effectiveness of our intervention is critically important because patients with undetected glaucoma and other eye diseases can suffer lasting visual impairment that can affect their quality-of-life, economic status, morbidity, and ultimately mortality. New strategies are necessary to improve patient access and utilization of eye care. Our study aims to determine if adherence to follow-up recommendations changes as a result of the enhanced intervention. We will determine the effectiveness of the intervention by examining the effect size associated with our intervention and specified outcomes (adherence to follow-up recommendations and vision-related quality-of-life).

**D.1.c. Adoption:** Our letters of support from Advisory Board members and partner institutions demonstrate a strong commitment and willingness to participate in this research study. We are working closely with primary care offices, health centers, universities, governmental agencies, and community organizations. We expect to notice variations in patient behavior based on the number of resources available to them. These varying settings and intervention modalities are critical to the current and potential impact of our intervention. If differences exist among sites, this is evidence of differential adoption.

**D.1.d. Implementation:** At each setting, implementation refers to the intervention agents' fidelity to all elements of the protocol. This includes consistency of delivery as intended and the time and cost of the intervention. Investigators in coordination with Westat and the project manager will determine the extent to which the intervention was delivered. We will assess implementation by reporting on the percentage of process objectives that were achieved, such as: What proportion of patients received the confirming diagnosis enrolled in the study? How many patients followed up with the general ophthalmologists at the initial 6-month, 1-year, 2-year, and 3-year visits. We will also conduct a cost analysis and report costs of all levels of the intervention, including recruiting patients, reading images, confirming diagnoses, randomization, and 3-year follow-up (Table 7).

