**Table 7: Tracking Measures Using *RE-AIM Framework* Approach**

RE-AIM	Evaluation Question	Tracking Measures	Data Source
Adoption	How were community partners and primary care settings engaged in the study?	# of participating community partners and primary care settings (offices, health centers). Primary care offices' satisfaction with participation.	Contact log  On-site observations On-site interviews

Reach	To what extent are high risk target populations being reached?	Patient characteristics (demographics, insurance status, ocular history, ocular risk factors).	Intake form/EMR
Implementation	How was the program implemented?	Patient navigator, cultural competency training conducted. # of staff at each onsite activity. # of patients who follow up with general ophthalmologists. Time taken per patient and for each eye exam. # of confirmatory diagnosis from fundus photos. # of referrals made based on NEI-VFQ.	Planning log  On-site observations  EMR
Efficacy/ effectiveness	Did the intervention work? (Comparison between intervention and control groups)	# of patients from each group adhering per year. Average percentage of visits attended per year. Clinical measures (visual acuity, IOP, VF). Health related quality-of-life (Visits 2 and 8). Satisfaction with eye services at each visit.	EMR  EMR NEI-VFQ Patient satisfaction survey
Maintenance	To what extent has the program been institutionalized?	Willingness of partners and PCPs to continue with telemedicine and community model.	On-site interviews

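### E.2.e tests the effect on IOP, visual acuity and NEI-VFQ only as a difference in linear slopes, which, depending on visit timing and the handling of baseline, can under-detect a sustained benefit and nearly miss a fading one

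*Combined protocol and SAP*

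**What the plan says.** Section E.2.e sets out the secondary analysis of the continuous outcomes: "Change in continuous clinical and quality-of-life measures (IOP, visual acuity, NEI-VFQ, etc) will be modeled using mixed effects linear regression". The mean model is "Fixed effects will be time (treated continuously), randomization assignment, treatment by time interaction, age, and diagnosis". For correlation, "A first-order autoregressive correlation structure will be assumed to model correlation among repeated measurements", and "When possible, random slope and intercept terms may also be included". The test is then fixed: "Effects of intervention on these measures will be tested by the significance of the interaction term".

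The arm main effect is in the model but is not tested. It is not stated whether the baseline value is a response row at time zero, is subtracted, or is a covariate.

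Three other places bear on this:

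- Section D.1.b says "We will determine the effectiveness of the intervention by examining the effect size associated with our intervention and specified outcomes", and the outcomes it lists include vision-related quality of life. It names no estimator.
- Section E.2.c, for the primary adherence outcome, uses Years 1, 2 and 3 and tests Year 1 separately from the average of Years 2 and 3.
- NEI-VFQ timing differs between sections. C.6.a says staff will "administer the validated NEI-VFQ-25 questionnaire at Visit 2, Visit 5 and Visit 8", and Table 5 agrees. Table 7 lists "Health related quality-of-life (Visits 2 and 8" only.

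**The concern.** The question is whether the intervention changes these outcomes. The planned test asks whether the arms diverge in a straight line over three years. The two questions coincide only if the effect grows in proportion to time. If the arms separate during early follow-up and then stay apart, part of the separation goes into the untested arm main effect. If the separation then shrinks, the slope can be close to zero although the intervention arm is better at every post-baseline visit.

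An early effect is plausible from the plan itself. Visit 3 is due within 4 weeks (C.9), and NEI-VFQ answers can lead to referrals (C.6.a). The primary analysis allows early and late effects to differ, but E.2.e does not, and gives no reason. At stake is a non-significant result on clinical and quality-of-life outcomes when a benefit exists.

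**Working it through.** **The plan's own power figures.** Table 10 covers adherence only; no power is given for IOP, acuity or NEI-VFQ. It reproduces. For 35% against 55%, n = 135 per arm, two-sided alpha 0.025:

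- null SE = √(2 × 0.45 × 0.55 / 135) = 0.0605, times 2.241 = 0.1357
- alternative SE = √((0.35 × 0.65 + 0.55 × 0.45) / 135) = 0.0593
- power = Φ((0.20 − 0.1357) / 0.0593) = Φ(1.08) = 86%

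All six rows agree with the table (86.1, 85.7, 86.1, 87.2, 89.1, 91.6%). So n = 135 per arm is a sound basis.

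**Inputs.** From the plan: 135 per arm (E.2.d), the mean model (E.2.e), Visit 3 within 4 weeks (C.9), and follow-up at 6 months and 1, 2 and 3 years (D.1.d). Assumed: SD 1, two-sided 0.05, a benefit of 0.35 SD (or 0.45 fading to 0.18 SD, counted from the first post-baseline visit), random-intercept share of variance 0.3-0.6, lag-1 residual correlation 0-0.6, complete data, and baseline as a response row. Visit months beyond those listed are also assumed.

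**Method.** Regress the visit-specific arm differences d on (1, t) by generalised least squares, with covariance 2V/135. Compare this with the mean post-baseline difference minus the baseline difference. Both leave the baseline difference free.

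**Hand check.** Take random-intercept share 0.5 and independent residuals. The slope is then Σ(t−t̄)d / S, with S = Σ(t−t̄)² and SE √(1 / (135 S)). The average contrast over m post-baseline visits has SE √((1 + 1/m) / 135). Power ≈ Φ(z − 1.96).

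1. IOP/acuity, months 0, 6, 12, 24, 36, sustained 0.35. t̄ = 15.6, S = 835.2. Slope = 0.35 × 15.6 / 835.2 = 0.00654 per month, or 0.235 over 36 months (67% of the benefit). SE 0.00298, z = 2.20, power 59%. Average contrast: 0.35 / 0.0962 = 3.64, power 95%.
2. IOP/acuity, months 0, 1, 13, 25, 36, full 0.35 already present at month 1. t̄ = 15, S = 966. Slope = 0.35 × 15 / 966 = 0.00543, SE 0.00277, z = 1.96, power 50%, against 95%.
3. Same months, effect starting only after the month-1 visit. Slope = 0.35 × (−2 + 10 + 21) / 966 = 0.01051, z = 3.79, power 97%. The average contrast falls to 0.2625 / 0.0962 = 2.73, power 78%.
4. NEI-VFQ, months 0, 13, 36, sustained 0.35. S = 664.7, z = 0.00860 / 0.00334 = 2.58, power 73%. Average contrast: 0.35 / 0.1054 = 3.32, power 91%.
5. NEI-VFQ, months 0, 18, 36, sustained 0.35. Slope = 0.35 × 18 / 648 = 0.00972, which is 0.35 over 36 months, so nothing leaks. Power 82% against 91%.
6. NEI-VFQ, months 0, 13, 36, with 0.45 at month 13 and 0.18 at month 36. Numerator −3.33 × 0.45 + 19.67 × 0.18 = 2.04, slope 0.00307, z = 0.92, power 15%. Average contrast: 0.315 / 0.1054 = 2.99, power 85%.
7. IOP/acuity, months 0, 1, 13, 25, 36, fading linearly from 0.45 at month 1 to 0.18. Numerator −14 × 0.45 − 2 × 0.357 + 10 × 0.265 + 21 × 0.18 ≈ −0.59, so the expected slope is negative.

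**Ranges over the covariance settings** (other combinations within the stated limits move the ends by several points):

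| Scenario | Slope test | Average contrast |
|---|---|---|
| IOP/acuity 0, 6, 12, 24, 36; sustained 0.35 | 46-69% | 87-99% |
| IOP/acuity, full effect at a 1-month visit; sustained 0.35 | 25-59% | 87-99% |
| IOP/acuity, effect after Visit 3; six-monthly visits | 71-98% | 79-95% |
| IOP/acuity, effect after Visit 3; annual visits | 83-99% | 64-86% |
| NEI-VFQ 0, 13, 36; sustained 0.35 | 59-82% | 80-99% |
| NEI-VFQ 0, 18, 36; sustained 0.35 | 68-93% | 80-99% |
| NEI-VFQ 0, 13, 36; fading 0.45 to 0.18 | 7-18% | 71-98% |

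**If the response is post-baseline change.** A sustained benefit is the same constant at every modelled visit, so its slope is exactly zero and the test rejects only at its false-positive rate. A fading benefit then has a slope of the wrong sign by construction.

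**The case against.** A reader might infer that the slope test generally misses a sustained benefit, or that a fading benefit will show the wrong sign. The documents do not support either as a general statement.

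- The worst IOP/acuity figures need the full effect to be present at a visit near month 1. C.9 has the provider examine the patient at Visit 3 and adjust therapy afterwards, so Visit 3 readings precede that adjustment. With the effect starting after Visit 3, the slope test is ahead on annual visits and roughly level on six-monthly ones, and the expected slope keeps the right sign under fading.
- For NEI-VFQ with baseline as a response row, the slope carries the whole of a sustained benefit when Visit 5 falls midway, or when only Visits 2 and 8 are used.
- Linear slope is a conventional summary for slowly progressive disease, and continuous time suits the patient-specific intervals in Table 6. No power is claimed for these outcomes.

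These points stand, and they rule out discarding the slope test. Nor is it established that the trial would report no effect, since D.1.b promises effect sizes. But D.1.b does not say which effect sizes, and the early/late contrasts in E.2.c cover adherence only. The first three rows of results in which the average contrast is clearly ahead do not all depend on a month-1 effect: the 6-month schedule and the NEI-VFQ fading case remain.

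**Conclusion.** The concern holds in a conditional form. E.2.e supplies one test, its null is equal linear slopes, and nothing else in the plan supplies a visit-specific or average contrast for these outcomes. On the D.1.d follow-up times a sustained 0.35 SD benefit loses about 30 to 40 points of power (46-69% against 87-99%). A fading NEI-VFQ benefit at months 0, 13 and 36 is almost undetectable (7-18% against 71-98%). The loss is small with Visit 5 near month 18, and largely absent for IOP/acuity if the effect begins after Visit 3. With baseline as a response row and fading from 0.45 to 0.18 SD, the expected slope has the wrong sign only if the full effect is already present at a visit near month 1. If post-baseline change is the response, the slope test cannot detect a sustained benefit at all.

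The powers rest on assumed effect sizes, covariances, visit months and complete data. The shares of benefit that reach the slope do not depend on effect size. Only secondary outcomes are concerned; the primary adherence test and Table 10 are unaffected.

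**What to change.** In E.2.e:

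1. State that baseline enters as a response row (or as a covariate).
2. Keep the slope test.
3. Add a model with time windows (baseline, Years 1, 2 and 3) and arm-by-window terms. Report the arm difference with its confidence interval at each year, and prespecify one average post-baseline contrast, in line with the Year 1 and Years 2-3 contrasts of E.2.c.
4. Where NEI-VFQ exists only at Visits 2 and 8, use the baseline-adjusted difference at Visit 8.
5. Reconcile C.6.a and Table 5 with Table 7 on when NEI-VFQ is analysed.

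The cost is wording: same data, same software. The downside is one more secondary contrast per outcome. The average contrast can have less power than the slope if the effect truly grows linearly, which is why the slope test stays.
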